### 7.1.1. Study Periods

Patient participation in the study will be defined by the four distinct study periods defined below:

- Screening (up to 28-days prior to start of Adagen® Lead in dosing) – This period starts at the time of the initial screening procedure through administration of the first dose of Adagen® in the lead in period. Note: patients will continue to receive his/her prescribed dose of Adagen® during this period.
- Adagen® Lead-in – This period starts with the initial dose of study-required Adagen® dosing through the start of EZN-2279 study treatment. This period will be a minimum of 3 weeks.
- EZN-2279 Study Treatment – This period starts with the initial dose of EZN-2279 through completion of at least 21 weeks of EZN-2279 dosing.
- EZN-2279 Maintenance – This period begins after completion of the EZN-2279 study period and continues until the end of the study (full regulatory approval of EZN-2279 or early study termination).

### 7.1.2. Recruitment and Enrollment

It is anticipated that patients will be enrolled in the study within approximately 12-months.

#### 7.1.2.1. Recruitment Definitions

Screening Failure – Patients who provide informed consent and do not proceed to study treatment (e.g., subject withdrawals consent, does not meet entry criteria). Screening data will be documented on the study specific Screening Log. Reasons for screen failure will be documented in the subject's source documents and on the Screening Log.

Enrolled Subject – Patients who pass pre-study (screening) evaluations and are assigned to study treatment.

Treated Subject – Patients who are enrolled and receive at least one dose of Adagen® during the Adagen Lead-In period.

Discontinued Subject – Patients who are treated but fail to complete through the end of the 21-week EZN-2279 treatment period.

Completed Subject – Patients who are treated and complete through the end of the 21-week EZN-2279 treatment period.

## 7.2. Study Treatments

### 7.2.1. Rationale for Dose Selection and Choice of Control Groups

Patients enrolled in this study will have ADA-SCID and be well-controlled on a weekly dose regimen of Adagen®. Patients will be maintained on the same weekly Adagen® dose during the Adagen® lead-in period but will be switched to a once weekly dosing regimen to permit assessment of Adagen® and EZN-2279 pharmacokinetics (only for patients  $\geq 10$  years of age) and trough levels. During the Adagen Lead-in Phase, Adagen® dose adjustments will be made if the patient does not meet criteria for dAXP levels ( $\leq 0.02$   $\mu\text{mol/mL}$ ) and ADA activity ( $\geq 15$   $\mu\text{mol/h/mL}$ ) specified in the inclusion criteria and the patient is considered to not be fully detoxified.

Following the Adagen® lead in phase, patients will be transitioned to receive an equivalent dose of EZN-2279. As 1 mg of EZN-2279 contains ADA enzymatic activity equivalent to 150 U of Adagen®, the equivalent dose will be calculated as follows:

$$\text{Adagen}^{\text{®}} \text{ dose (U/kg)} \times 1\text{mg EZN-2279}/150\text{U Adagen}^{\text{®}} = \text{EZN-2279 dose (mg/kg)}$$

## 7.3. Assignment of Patients to Treatment

This is a non-randomized study. Each patient who completes the study screening assessments, meets all eligibility criteria, and is accepted for study participation will be assigned a unique patient number and begin Adagen® lead-in treatment followed by EZN-2279 treatment and maintenance periods.

## 7.4. Study Duration

The primary analysis of data for efficacy, PK, immunogenicity, clinical status, and safety will be performed when the Week T-21 (at least 21 weeks of EZN-2279 treatment) data is available for the last patient enrolled in the study.

### 7.4.1. Duration of Treatment and Patient Participation

All patients will receive a minimum of a 3-week Adagen® lead-in followed by 21-weeks of study treatment with EZN-2279. Patients will be given the opportunity to remain on EZN-2279 maintenance until the study is concluded (full regulatory approval of EZN-2279 or early study termination). Assuming a 12 month enrollment period and 18 months for the submission of data and regulatory approval of EZN-2279, the initial patient enrolled will receive study treatment for approximately 3 years and the last patient enrolled will receive study treatment for approximately 2 years.

Patient participation will be approximately 8-weeks longer than the treatment duration (4 week screening period and a 30-day post treatment safety follow-up of patients who discontinue study drug early).

## 7.5. Methods Used to Minimize Bias

Due to the single-arm, one way crossover study design used, blinding is not possible.

Laboratory assessments performed for pharmacokinetics (only for patients  $\geq 10$  years of age), safety and efficacy are objective data provided by central laboratories and are not subject to bias.

Physical examination and adverse event assessments are subjective assessments that are subject to bias due to the inability to blind study staff to the identity of study treatments administered.

## 7.6. Appropriateness of Study Measurements

In this study, for patients  $\geq 10$  years of age, pharmacokinetics will be assessed by repeated sampling for ADA activity following a dose and pharmacodynamics will be assessed by monitoring dAXP levels. These are assessments that are commonly used to monitor patients treated with Adagen®.

Safety in this study will be assessed by monitoring adverse events, laboratory parameters (serum chemistry, hematology, and urinalysis), physical examination changes and vital signs. These are standard assessments for monitoring safety in clinical trials. In addition, monitoring of binding and neutralizing antibodies is commonly used to monitor patients treated with Adagen®.

In addition to pharmacodynamics, efficacy will be assessed by monitoring trough ADA activity, immune status (ALC, lymphocyte subset analysis, quantitative immunoglobulins) and clinical evaluations (growth, incidence of infections and hospitalizations). These are assessments that are commonly used to monitor patients treated with Adagen®.

## 7.7. Study Monitoring Committees

An independent Data and Safety Monitoring Committee (DSMC) will be set up to monitor the conduct of the study. The DSMC will review the safety information after the initial three patients have been treated with weekly administrations of EZN-2279 through completion of the full PK sampling assessments (Week T-9), after all 6 patients have been treated with weekly administrations of EZN-2279 through completion of Week T-9, after all patients complete the EZN-2279 Treatment Phase (i.e., Week T-21) and when all patients completed 1 year (i.e, 2 maintenance cycles) of treatment with EZN-2279. At minimum, the DSMC will review safety, PK (ADA activity), and erythrocyte dAXP data during the study.

A Charter for the DSMC will be written as an independent document.

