Adagen® will be discontinued and therapy with an equivalent dose of EZN-2279 will be initiated. In the EZN-2279 treatment phase of the study, patients will receive a single i.m. dose of EZN-2279 weekly for 21 consecutive weeks. Prior to receiving the initial dose of EZN-2279, patients will have the following procedures performed: physical examination, vital signs, growth assessment, performance status, safety laboratory assessments (hematology, chemistry, urinalysis), and have blood samples obtained for assessment of lymphocyte subset analysis, quantitative immunoglobulins, EZN-2279 and Adagen® antibody titers (neutralizing and binding antibodies) and anti-PEG antibodies. Trough total erythrocyte dAXP concentration and trough plasma ADA activity will be measured prior to dosing at weeks T-1, T-3, T-5, T-7, T-8 and every other week from Week T-9 through Week T-21. At week T-8 the patient will have dAXP levels and ADA activity assessed to assure the dose of EZN-2279 administered maintains dAXP and ADA activity at protocol specified levels. If these levels are not met and the patient is not considered fully detoxified, the patient will undergo a dose adjustment and be reassessed prior to entering the EZN-2279 full PK sampling week (Week T-9). During study week T-9, plasma ADA samples for full PK evaluation will be collected at Week T-9 (Days 58-63). Physical examination and safety laboratory assessments will be performed every 4 weeks (Weeks T-5, T-9, T-13, T-17 and T-21). Blood samples obtained for assessment of lymphocyte subset analysis, quantitative immunoglobulins, EZN-2279 antibody titers (i.e., neutralizing and binding antibodies) and anti-PEG antibodies will be obtained at selected timepoints during the EZN-2279 treatment period.

Following completion of the EZN-2279 treatment period, patients may enter the EZN-2279 maintenance period. During this phase of the study patients will continue to receive single i.m. doses of EZN-2279 weekly. The following assessments will be performed during study visits every 3 months: physical examination, vital signs, growth assessment, performance status, safety laboratory assessments (hematology, chemistry, urinalysis), and have blood samples obtained for

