#### **11.4. EZN-2279 Maintenance Period**

As part of standard clinical care, the following evaluations will be performed during visits approximately every 3 months (13 weeks  $\pm$ 3 weeks) until study completion. For example, based upon the start of EZN-2279 treatment (Day 1, Week T-1), maintenance visits would be scheduled to occur on Weeks 34 (Cycle 1), 47 (Cycle 2), 60 (Cycle 3), 73 (Cycle 4), 86 (Cycle 5), 99 (Cycle 6), 112 (Cycle 7), 125 (Cycle 8), 138 (Cycle 9), 151 (Cycle 10), 164 (Cycle 11), 177 (Cycle 12), 190 (Cycle 13)  $\pm$ 3 weeks from start of EZN-2279 treatment.

The patient will have the following procedures performed at each maintenance visit prior to EZN-2279 dosing:

- Physical examination
- Height and weight for growth assessment
- Performance status
- Vital Signs
- Safety Lab
  - Hematology
  - Chemistry
  - Urinalysis
- Other labs – blood samples will be obtained 15 to 30 minutes prior to dosing for:
  - dAXP
  - Trough ADA activity
  - B-, T-, and NK-lymphocyte subset analysis
  - Quantitative immunoglobulins
  - EZN-2279 antibody titers (i.e., neutralizing and binding antibodies) and anti-PEG antibodies
- Adverse event assessment
- Assessment of infectious complications and hospitalizations
- Review of EZN-2279 administration diary card and returned vials for assessment of treatment compliance
- Assessment of concomitant medications and procedures since last study visit

- Assessment of overall survival

An appropriate supply of EZN-2279 will be dispensed along with a medication compliance diary card. Note that it is not necessary to dispense a full 13 week supply during a maintenance visit; quantities of EZN-2279 dispensed will be at the discretion of the Investigator based upon the patient's proximity to the study site and medication compliance.

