### 13.2.3. Data Analysis

Statistical analysis will be conducted by Leadiant Biosciences, or its designee. The primary analysis of study data will be performed after the last patient has completed through the EZN-2279 treatment phase (Study Week T-21). Once the last patient enters the EZN-2279 maintenance phase, data will be analyzed after all patients complete 6-months of EZN-2279 maintenance (EZN-2279 treatment week 47) and annually thereafter. The analysis of study data will be repeated upon study completion.

Efficacy and safety analyses will be performed using Statistical Analysis Systems® (SAS®) Version 9 or later (SAS Institute, Cary, NC), or comparable software.

A complete description of data handling rules and planned statistical analyses is detailed in a separate Statistical Analysis Plan (SAP). Unless otherwise specified in this document or in the SAP, baseline is defined as the last measurement for a variable before the initial dose of study drug (EZN-2279 or Adagen®), and missing data will generally not be imputed. If applicable, hypotheses will be tested at a two-sided statistical significance level of 0.05.

Analyses will be primarily descriptive, with data listings, graphical presentations, frequency tabulations, and summary statistics as appropriate.

Each patient will serve as his/her own control based on the baseline assessment of each endpoint as appropriate, including changes in body weight as percentile on the growth curve, antibody formation, etc.

Additional statistical analyses, other than those described in this section, may be performed if deemed appropriate to further explore the study data.

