10. RULES AND DEFINITIONS

10.1 Timing of Analyses

The initial three patients will be enrolled and complete through full EZN-2279 pharmacokinetic sampling (Week T-9). An independent data and safety monitoring committee (DSMC) will review safety, PK (ADA activity), and erythrocyte dAXP data. If no concerns are noted, enrollment will continue for the remaining three patients. A similar DSMC review will occur for EZN-2279 dosing for the following:

- All six patients who complete through (Week T-9).
- All six patients who complete through (Week T-21).
- All six patients who complete one year (i.e. two maintenance cycles).

Listings will be produced for the BLA when three subjects have complete data through final analysis (one year/two maintenance cycles). The BLA will include all patients enrolled at that time.

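### The one-year DSMC review and SAP final analysis are set at two maintenance cycles, which is Week 47 and nominally 43 days short of a year of EZN-2279

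*Protocol*

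**What the plan says.** Protocol 7.7 lists the DSMC reviews. The last takes place "when all patients completed 1 year (i.e, 2 maintenance cycles) of treatment with EZN-2279". The year is stated as exposure to EZN-2279, so the Adagen lead-in does not count towards it.

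The SAP repeats the equation. Sections 3.1 and 10.1 give the DSMC milestone as "All six patients who complete one year (i.e. two maintenance cycles". Sections 6.1 and 7.1 attach the same definition to the final analysis, which 6.1 calls the fourth look. Section 10.1 also uses the label in its trigger for the BLA listings.

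The calendar is set elsewhere. Protocol 7.1 says that in the treatment phase "patients will receive a single i.m. dose of EZN-2279 weekly for 21 consecutive weeks". Protocol 11.4 then has "visits approximately every 3 months (13 weeks", with a three-week tolerance either way, and gives as its example that "maintenance visits would be scheduled to occur on Weeks 34 (Cycle 1), 47 (Cycle 2), 60 (Cycle 3", and so on to Cycle 13. It counts the tolerance in "weeks from start of EZN-2279 treatment". Protocol 13.2.3 gives Week 47 a different name: "data will be analyzed after all patients complete 6-months of EZN-2279 maintenance (EZN-2279 treatment week 47".

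**The concern.** One visit carries two labels. Protocol 7.7 and the SAP call the end of two maintenance cycles one year of EZN-2279. Protocol 11.4 and 13.2.3 call it Week 47 and six months of maintenance. Both descriptions can hold only if 21 weeks plus two 13-week cycles make a year, and they do not.

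The milestone triggers a DSMC review and the SAP's final analysis. If the label is carried into a report, the minimum follow-up will be overstated. Someone who builds the cut from 52 weeks of exposure will also take different data from someone who builds it from the cycle count. With about six evaluable patients and no earlier clinical study of EZN-2279 (protocol 5.3.2), a few weeks per patient is a visible share of the long-term safety record.

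**Working it through.** **Inputs**
- Treatment phase: 21 weeks, with Week T-21 on Day 141 (protocol 7.1, 11.3.22).
- Maintenance cycle: 13 weeks (11.4).
- Visit window: ±3 weeks, counted from the start of EZN-2279 (11.4).
- One year: 365 days.

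**Reproducing the plan's schedule**
- Week of cycle k = 21 + 13k. For k = 1 to 13 this gives 34, 47, 60, 73, and so on to 190, which are exactly the weeks listed in 11.4. Week 47 is therefore not a typing slip.
- Day of Week w = 7(w − 1) + 1. This returns Day 57 for T-9 and Day 141 for T-21, as printed.

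**Exposure at two cycles**
- Week 21 + 2 × 13 = 47. Day 7 × 46 + 1 = 323, so 322 days have elapsed (46 weeks, 0.88 year, about 10.6 months).
- Nominal shortfall: 365 − 322 = 43 days, about 6 weeks.
- Anchored window: 322 ± 21 = 301 to 343 days, a shortfall of 64 to 22 days.
- More generous count, crediting the whole of Week 47: 47 × 7 = 329 days, window 308 to 350, a shortfall of 57 to 15 days (36 nominal).

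**Routes that could close the gap**
- *Visit-to-visit window.* The schedule footnote in both documents gives an interval of 13 weeks ± 3 with no anchor. Two longest intervals give 21 + 2 × 16 = Week 53, Day 365: 364 days elapsed, exactly 52 weeks.
- *Repeat of Weeks T-5 to T-8 (11.3.8.1).* One repeat adds 4 weeks. If maintenance visits follow the actual end of treatment, two cycles fall at 25 + 26 = Week 51 (350 days, 15 short), or Week 54 at the late edge of the window (371 days).

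**Who carries the shortfall at an all-patients cut**
- Protocol 7.1 holds further enrolment until the first three patients complete Week T-9 sampling and the DSMC has reviewed them. That is about 63 days after the third patient's first dose. The lead-in is at least 3 weeks (21 days), so patient 4 starts EZN-2279 at least about 63 + 21 = 84 days after patient 3.
- When patient 4 reaches Cycle 2, patient 3 is at about 301 + 84 = 385 days on the earliest allowed visit, or 322 + 84 = 406 on the nominal one.

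**First visit that always passes a year (anchored schedule)**
- Cycle 3, Week 60: 59 × 7 = 413 days, window 392 to 434.

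**The case against.** Four points can be made for the plan.

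- *The milestone can be carried out as written.* Each statement adds the cycle count, 11.4 maps Cycle 2 to Week 47, and 13.2.3 prints that week. This largely stands: sites and the DSMC can identify the visit, and a separate DSMC charter, not available here, may say more. It does not make the word year correct.
- *The consequences are small.* No objective or endpoint is defined at one year, efficacy is descriptive, dosing continues, and 13.2.3 plans annual analyses and a repeat at study completion. This stands and limits the weight of the point.
- *Completing two cycles might mean running up to the Week 60 visit.* Protocol 13.2.3 goes against this, since it treats six months of maintenance as completed at Week 47.
- *Some patients will have a year.* This also stands. A reader might infer that no patient need have a year of exposure at this cut. The documents do not support that for the all-patients cut: staggered enrolment puts the first three at about 385 days or more unless they discontinue, and nothing truncates their data at their own Cycle 2 visit.

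A reader might also infer that no permitted Cycle 2 visit can reach 52 weeks. That holds only on the anchored window. The week list in 11.4 is introduced as an example, and the unanchored footnote allows Week 53 at its extreme. A repeat of Weeks T-5 to T-8 can also carry an adjusted patient past a year. Neither route helps an unadjusted patient on the nominal schedule, and the milestone is stated for all patients.

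**Conclusion.** The one-year label is wrong on the protocol's own calendar. A patient on the nominal schedule has 322 days of EZN-2279 at the milestone, 43 short of a year, and 22 to 64 short across the anchored window. The shortfall falls on the last patients to reach the milestone, so the condition that all patients have completed one year is not delivered.

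This rests on two assumptions: that the window is anchored to the start of EZN-2279, as 11.4 words it, and that Weeks T-5 to T-8 are not repeated. The statement about the first three patients assumes that they remain on treatment and that the enrolment hold is observed. The documents do not show whether a year or two cycles was intended.

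This is an error in the definition and label of one review and one analysis. It does not touch the primary endpoint at Weeks T-15 to T-21.

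**What to change.** In protocol 7.7 and SAP 3.1, 6.1, 7.1 and 10.1, restate the milestone as *Week 47 (two maintenance cycles, about 10.6 months of EZN-2279)*, which agrees with protocol 11.4 and 13.2.3. Report each patient's actual exposure at the cut, and do not call the result one-year data. SAP 7.2 already summarises overall EZN-2279 duration and lists administration, so this is a wording change with no new data and no delay.

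If the sponsor wants a one-year statement for all patients, define the cut as at least 52 weeks since each patient's first EZN-2279 dose. On the anchored schedule, Cycle 3 (Week 60) is the first visit whose whole window meets that. The cost is a delay of about 13 weeks to that one analysis.

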## 8. STUDY DRUG AND TREATMENTS

### 8.1. Description of Study Drug(s)

EZN-2279 and Adagen® are isotonic, pyrogen-free, sterile solutions in phosphate-buffered saline. Adagen pH is 7.2 to 7.4. EZN-2279 pH is 6.7 to 7.1., both solutions are clear and colorless, contain no preservatives and designed for i.m. injection only.

Both drug products (EZN-2279 and Adagen®) are manufactured by Leadiant Biosciences, Inc., Indianapolis, IN.

### 8.2. Supply and Labeling

#### 8.2.1. How Supplied

Leadiant Biosciences will supply sufficient quantities of EZN-2279 and lead-in Adagen® for the study.

##### 8.2.1.1. EZN-2279

EZN-2279 will be supplied in 1.5 mL single-use vials containing 2.4 mg of EZN-2279 (1.6 mg/mL). Vials of EZN-2279 will be boxed individually.

**8.2.1.2. Adagen®**

Adagen® will be supplied in boxes of four 1.5 mL single-use vials (NDC-57665-001-01). Each vial contains 375 units of Adagen® (250 units/mL).

**8.2.2. Labeling**

**8.2.2.1. EZN-2279**

EZN-2279 will be labeled in accordance with FDA requirements for a clinical investigational study.

Each vial of EZN-2279 provided to the study site will contain a label with the wording as noted in the example below on both the box and vial; however, the layout of the wording and the size of the label affixed to the drug vial may be different.

|  |
|--|
| 
Protocol STP-2279-002
Contents: EZN-2279 Sterile–For intramuscular use only. Each 1.5-mL single-dose vial contains 2.4 mg (1.6 mg/mL).
Storage: +2°C to +8°C (36°F to 46°F) Protect from light REFRIGERATE - DO NOT FREEZE
Caution: New Drug - Limited by Federal (United States) law to investigational use.
Lot No.: _____
Manufactured _____
Manufactured for: Leadiant Biosciences, Inc., [name]
 |
|--|

**8.2.2.2. Adagen®**

Adagen® will be labeled with the standard labeling of the commercially available product.

For inventory control purposes, a secondary label will be added to each box of Adagen® to designate Adagen® supplied by Leadiant Biosciences only for study use.

A sample label is provided below.

|   |
|---|
| 
Protocol STP-2279-002
Only for use for patients enrolled in Protocol STP-2279-002
 |
|---|

**8.3. Storage Conditions**

**8.3.1. EZN-2279**

EZN-2279 should be stored refrigerated at +2°C to +8°C (36°F to 46°F). Do not freeze. EZN-2279 should not be stored at room temperature. EZN-2279 should not be administered if it has been shaken or vigorously agitated. EZN-2279 should not be used if there are any indications that it may have been frozen.

EZN-2279 should be protected from light. Avoid excessive or prolonged light exposure when storing EZN-2279.

**8.3.2. Adagen®**

Adagen® should be stored refrigerated at +2°C to +8°C (36°F to 46°F). Do not freeze. Adagen® should not be stored at room temperature. Adagen® should not be administered if it has been shaken or vigorously agitated. Adagen® should not be used if there are any indications that it may have been frozen.

---

